Appendix A: Relevant Literature on Infusion Sets

A.1 Failure Modes and Failure Rates for Current Infusion Sets 1295 1296 The nationwide pediatric surveillance of insulin infusion sets in Germany and Austria reported that 192 (29%) patients had no infusion set issues at all. However, the other 475 (71%) patients reported 1,404 1297 1298 events. The most often reported device adverse event was cannula obstruction (32.9%). A total of 14.2% of the patients reported that they had blood in the insulin infusion cannula: 11.1% had skin with redness 1299 and 10.1% reported cannula kinking. 36.2% of the reported complications occurred by day 1 of infusion 1300 1301 set usage and 82.4% by the end of day 2.15 Pfützner et al. performed a prospective randomized controlled crossover clinical trial to investigate the 1302 tolerability of 2-day use of commercial insulin infusion sets in comparison to 4-day use in a real-world 1303 1304 setting. Twenty-four patients with T1D managed with an insulin pump were studied during two 3-month periods. The number of cannula-related adverse events was 290 with 2-day use versus 495 with 4-day use 1305 (P < .05). The overall number of treatment related events was 750 with 2-day use versus 934 with 4-day 1306 1307 use (P < .001). There was no difference in glycemic control between the treatment arms. Treatment satisfaction was higher with 2-day use (very high/high satisfaction: 90.4% versus 4 day-use: 77.3%, P < 1308 .05). The authors concluded that using an infusion set for a longer than 2-3 days resulted in a clinically 1309 relevant increase in treatment-related tolerability problems. 16 1310 1311 Renard et al. performed a prospective, two-period, observational, multicenter study in 45 T1D outpatients. During the initial 1-month period the patients used a Teflon cannula (98% of cases) 1312 and crossed over to an investigational insulin infusion set (Accu-Chek FlexLink, Disetronic Medical 1313 1314 Systems AG) for a 3-month period. Forty-five initial infusion failures occurred in 14 patients among 507 commercial Teflon cannula insertions (8.9% of cases), whereas 15 failures were seen in nine 1315 patients during 488 investigational cannula insertions (3.1% of cases) (P<0.001). The overall rate of late 1316 cumulative events was 113 of 507 (22%) with the commercial infusion set versus 66 of 488 (14%) using 1317 the investigational infusion set (P<0.001). The occurrence of pain, skin reaction, or redness at the infusion 1318 1319 site was lower using the investigational insulin infusion cannula.¹⁷ 1320 Van Bon et al. conducted a multi-center trial of 256 patients on three insulins. Approximately 30% of 1321 patients experienced at least 1 perceived set failure during the 13-week study period with each insulin. More than 60% of patients experienced unexpected hyperglycemia during the 13-week study period. 1322 These results are similar to experts' experience managing T1D using an insulin pump and currently 1323 available infusion sets. Improving the reliability, enhancing the comfort and extending the duration of 1324 infusion set use each would be important contributions to continuous subcutaneous insulin infusion 1325 therapy.¹⁸ 1326 In a pilot study in 22 patients by Lal et al. conducted at Stanford University, the most common reason for 1327 infusion set removal was adhesive failure (50%), followed by hyperglycemia unresponsive to a correction 1328 bolus (33%), hyperglycemia with elevated ketones (8%), and infection of the insertion site (8%). 1329 A.2 Effect of Wear Time on PK/PD and Test Meal Response 1330 Clausen et al. observed progressive acceleration of PK exposure over 4 days of wear time¹⁹, and 1331 confirmatory evidence was provided by Swan et al.²⁰, who demonstrated progressive acceleration of 1332 PD over 3 days of catheter wear time. This was further confirmed by Vaughn and Muchmore.²¹ 1333 Luijf et al. tested glucose response to a test challenge and showed substantial declines in glucose response 1334 between day 1 and day 3 of catheter wear.²² This improved glucose response was seen for both patch 1335 (tubeless) and conventional insulin pump systems, which was presumably a result of improved early 1336 insulin exposure that occurs over the first 3 or so days of catheter wear time. 1337

1338 Simic et al. performed a clamp study with 16 subjects assessing a new extended-wear infusion set with an anti-inflammatory coating and Lantern technology (ConvaTec) and found that while insulin absorption 1339 decreased over wear time, it was also significantly faster 4 and 7 days after insertion. None of the patients 1340 experienced severe hypoglycemia over a period of 7 days. The authors claim that increased rate of 1341 absorption my facilitate better postprandial control.²³ 1342 1343 A.3 Experience with Extended Wear (>3 days) Patel et al. performed a randomized crossover clinical trial to compare the performance of Teflon versus 1344 stainless steel insulin infusion sets in ambulatory humans for up to 1 week. The subjects used a Quick-Set 1345 1346 or a Sure-T CSII cannula until the infusion set failed or was worn for 1 week. After 7 days, both types of infusion sets had a 64% failure rate. Eighty-seven percent of the steel sets and 77% of the Teflon sets 1347 were functioning after 3 days (this number includes the 15% that failed on the first day because of 1348 1349 kinking), after 5 days 68% of the steel and 59% of the Teflon sets were functioning, after 6 days 53% of the steel and 46% of the Teflon sets were functioning, and at the end of 7 days 32% of the steel and 32% 1350 1351 of the Teflon sets were functioning. Overall, 30% failed because of hyperglycemia and a failed correction dose, 13% were removed for pain, 10% were pulled out by accident, 10% had erythema and/or induration 1352 of >10 mm, 5% fell out because of loss of adhesion, and 4% were removed for infection. The main 1353 1354 predictor of length of wear was the individual subject. There was no increase in hyperglycemia or daily 1355 insulin requirements when an infusion set was successfully used for 7 days.²⁴ Waldenmaier et al. tested extended wear (≥7 days) of commercial steel and Teflon insulin infusion sets in 1356 40 adult subjects on insulin pump therapy. 66% of 160 inserted infusion sets were used for 7 days with no 1357 1358 obvious difference between steel and Teflon infusion sets (mean wear time was 6.2 days). The main reasons for early infusion set replacements were occlusions (19%), adhesive issues (4%), and accidental 1359 removal (4%). Comparing glycemic control during day 1-3 and 1-7, there was no difference in mean BG 1360 and insulin dose. The authors concluded that infusion set replacement intervals may be individualized 1361 beyond the currently labeled maximum use duration.8 1362 Lal et al. assessed longevity of the previously mentioned ConvaTec infusion set in a pilot study including 1363 22 subjects. 45% of the novel infusion sets lasted 10 days, with a median wear time of 9.1 days. While the 1364 mean BG concentration increased significantly over time, the total daily insulin dose did not change 1365 throughout 10 days of set wear.⁹ 1366 Recently, Medtronic reported an overall wear period success rate of 74.8% at 7 days using an extended 1367 wear infusion set (Buckingham et al., poster, American Diabetes Association annual meeting, 2021), 1368 leading to device approval by the FDA (510k). There has been no marketing experience reported for 1369 this device. 1370 1371 Summarizing these various studies of cannula wear time, it appears that currently marketed infusion sets 1372 have limited life span, and room for improvement is present.

	5.8.3	Insulin Metrics by Day of Infusion Set Wear	9
6	Desc	ription of Statistical Methods	10
	6.1	Analysis Cohorts	10
	6.2	Analysis of the Primary Endpoint	10
	6.3	Analysis of the Secondary Endpoints	10
	6.3.1	SteadiSet IIS Success Rate	10
	6.3.2	CGM Endpoints	10
	6.3.3	Insulin Endpoints	11
	6.3.4	Pump Endpoints	11
	6.3.5	Tolerability Endpoints	11
	6.4	Analysis of the Exploratory HbA1c Endpoint	12
	6.5	Usability, Satisfaction & Preference Survey	12
7	Safet	y Analyses	12
8	Inter	vention Adherence and Retention Analyses	12
9	Base	line Descriptive Statistics	13
10	Plani	ned Interim Analyses	13
11	Subg	roup Analyses	14
12	Mult	iple Comparisons	14
13	Addi	tional Tabulations and Analyses	15
14	Refe	rences	15

1 Study Overview

- 2 This document outlines the statistical analyses to be performed for the SteadiSet Insulin Infusion
- 3 Set study.

1

- 4 This is an unblinded, single arm, prospective, multicenter study to assess the efficacy and safety
- 5 of the SteadiSet insulin infusion set (IIS) while using a Tandem pump with t:slim X2 Control-IQ
- 6 in adults with type 1 diabetes (T1D). Enrollment will proceed with a goal of 240 participants
- 7 completing the trial, ~120 who will use HumalogTM (insulin lispro) and ~120 who will use
- 8 NovoLogTM (insulin aspart). Participants will be recruited from up to 20 clinical sites, each
- 9 contributing a maximum of 25 participants. All participants will use the SteadiSet IIS with the
- study pump for 12 wear periods of up to 7 days each. The efficacy analysis will include
- participants who complete at least 1 wear period. The safety analysis will include all enrolled
- 12 participants.

13 **2** Consistency

- 14 This SAP does not conflict with the study protocol statistics chapter (version indicated on the
- 15 title page). Additional analyses and tabulations have been included in this Statistical Analysis
- 16 Plan that are not included in the protocol.

17 **3 Statistical Hypotheses**

- 18 The primary outcome is percent of successfully inserted SteadiSet IIS that are not withdrawn
- from use prior to 7 days (168 hours) due to the reasons listed in section 5.2.
- 20 The null/alternative hypotheses are:
- Null Hypothesis: The success rate is 75%.
 - Alternative Hypothesis: The success rate is different from 75% (two-sided).

23 4 Sample Size

22

31

- 24 The study is projected to enroll up to 300 participants such that 240 complete the trial: ~120 who
- will use Humalog[™] (insulin Lispro) and ~120 who will use NovoLog[™] (insulin aspart).
- Assuming N=120 participants completing the study for each insulin type, a null hypothesis
- stating that the success rate is 75%, a true success rate of 83%, 12 wear periods per participant,
- 28 within-participant correlation of at most 0.4, and two-sided type 1 error rate of 5% we will have
- statistical power of 87% for the evaluation of each of the two insulin types. Note that with only 9
- wear periods per participant we would still have 86% power.

5 Outcome Measures

- 32 The Primary and Key Secondary Efficacy endpoints will be analyzed by infusion set. If more
- than one type of insulin is used during an infusion set wear period, that wear will be excluded
- 34 from analyses of the Primary and Key Secondary Efficacy endpoints. When the other Secondary
- outcomes or the Exploratory outcome are analyzed separately by insulin type, any wear period

- during which more than one type of insulin is used will be excluded from the analysis, except
- where specified.

38 5.1 Clinical Events Committee

- 39 Clinical Primary Efficacy and Key Secondary events will be adjudicated by the Clinical Events
- 40 Committee (CEC). The CEC's composition and role are described in the Clinical Events
- 41 Committee SOP and Charter.

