479 Subjects will be instructed to insert a new sequential infusion set following removal of each prior set until 12 infusion sets have been used. Sets that fail in the first 8 hours of use will be replaced 480 and will not count toward the target of 12 infusion sets worn. 481 Subjects will be instructed to change the insulin cartridge every 48-72 hours, as recommended by 482 their healthcare provider. 483 484 Subjects will be instructed to change their insulin cartridge and infusion set independent of each other and follow instructions in the Participant Guidebook and IFU. Subjects will be instructed to 485 contact study site if there is concern about infusion set failure. 486 Subjects will be required to upload insulin pump data (which includes both insulin dosing and 487 CGM data). This will be performed remotely for virtual visits or in clinic for face-to-face visits. 488 Ketone and BG meters will be uploaded during face-to-face visits. 489 Subjects who have only virtual visits will be provided with three ketone and BG meters each, and 490 will be instructed to mail the meters to the study site at week 2, week 6 and final visits. 491 3.2 Hyperglycemia Management Guidelines 492 The study pump's Control-IQ High Alert, which cannot be disabled, will alert the subject when there is 493 a CGM reading >200 mg/dL and no prediction the CGM will decrease in the next 30 minutes. 494 495 The study pump's optional CGM High Alert will be configured by study staff with a threshold of 250 mg/dL and a Repeat setting of 60 minutes, so the alert recurs every 60 minutes as long as the 496 hyperglycemia persists. High BG reminder should be set to OFF. 497 The pump will have the "out of range" alert set for 20 minutes (shortest possible setting) to reduce risk of 498 499 missing data. The pump "low insulin alert" will be set at ≥ 20 units to reduce risk of running the pump on an empty cartridge. It is recommended to set the Auto Off Alert to OFF. Site Reminder alert may be set to 500 ON to remind subjects to change their cartridge but not their infusion set. 501 502 Subjects will be instructed not to modify the alert settings configured by study staff that are described above. 503 Subjects will receive training on how to address Occlusion alarm #1 (resolvable alarm) and Occlusion 504 alarm #2 (non-resolvable alarm) requires infusion set change. 505 Study subjects will be provided a written Hyperglycemia Management Guidelines that will specify the 506 steps to take in case of prolonged hyperglycemia, testing of blood glucose, ketones, and correction 507 boluses. 508 509 3.3 Hypoglycemia Management Hypoglycemia will be managed by the Study subjects as they would as part of their usual diabetes 510 management. Hypoglycemia alarms may be set at the discretion of the study subject. 511 3.4 Daily Text 512 Subjects will receive a daily reminder text indicating the target date and time of infusion set removal. 513 The daily text will provide a link to a questionnaire for the subject to complete with each infusion set 514 insertion and removal providing specifics about all infusion set changes. 515 3.5 Follow-up Visit and Contact Schedule 516 517 Subjects will have the following scheduled follow-up visits and phone contacts as follows:

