
919	6.6.2 Criteria for Suspending or Stopping Overall Study
920	In addition to the suspension of device use due to a UADE as described in Section 6.6.1, study activities
921	could be similarly suspended if the manufacturer of any constituent study device requires stoppage of
922	device use for safety reasons (e.g., product recall). The affected study activities may resume if the
923	underlying problem can be corrected by a protocol or system modification that will not invalidate the
924	results obtained prior to suspension.

925	Chapter 7: Miscellaneous Considerations
926	7.1 Drugs Used as Part of the Protocol
927 928	Subjects will use their personal insulin, either insulin lispro (Humalog) or insulin aspart (NovoLog), throughout their study participation.
929 930	In the event a subject's insulin changes from Humalog to NovoLog, or vice versa, it will be noted in the case report form and analysed accordingly.
931	7.2 Collection of Medical Conditions and Medications
932 933 934	Pre-Existing Condition : Any medical condition that is either present at screening, a chronic disease, or a prior condition that could impact the Subject's health during the course of the study (e.g., prior myocardial infarction or stroke).
935 936 937 938 939	Medical Conditions during the study : In addition to conditions meeting the reporting requirements for an adverse event or device issue as described above, the following medical conditions should also be reported: (1) new diagnosis of a chronic disease (i.e., not present at the time of enrollment), and (2) any medical condition that could affect the subject's ability to carry out any aspect of the protocol or could affect an outcome assessment. New conditions or worsening of a previous medical condition should be reported as adverse events.
941 942	Medications : All medications for the treatment of pre-existing conditions at screening and/or adverse events, or other medications that could impact blood glucose, should be recorded.
943	7.3 Prohibited Medications, Devices, Treatments, and Procedures
944 945	Treatment with any insulin other than insulin lispro and insulin aspart and treatment with any non-insulin glucose lowering agent besides metformin is not permitted.

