1011 1012	2.	Evidence of infusion set site infection defined as requiring treatment or at the investigator's judgment	
1013 1014	3.	Cannula dislodgement from subcutaneous (SC) space (with or without liquid leakage at the cannula insertion site)	
1015 1016		 Leakage at the cannula insertion site may or may not be deemed by the investigator to constitute infusion set failure following consultation with the study subject 	
1017 1018		b. Accidental removal events (e.g., tubing caught on doorknob) are excluded from this proportion calculation	
1019	4.	Occurrence of a non-resolvable pump occlusion alarm,	
1020 1021	5.	Other device malfunction (e.g., inability to pierce skin, bending, or other malformation that might impact insulin infusion, securement failure)	
1022	6.	Presence of pain of sufficient severity to prompt early removal of infusion set	
1023 1024	7.	Any other event that can be ascribed to the investigational device performance that results in failure of insulin delivery	
1025		8.4.5 Other Secondary Endpoints	
1026 1027	1.	Standard glucose control measures obtained from CGM, including observed hyper- and hypoglycemic episodes, time in range, mean 24-hour glucose, and other measures	
1028 1029	2.	Total daily insulin dose, basal dose, bolus dose, and bolus basal ratio, overall, and by day of infusion set wear.	
1030 1031	3.	Subject tolerability levels for the infusion set insertion as assessed by a pain scale of 0 to 100 with zero being no pain and 100 being significant pain	
1032	4.	Hyperglycemia trends in days 1-3 versus after day 3	
1033 1034 1035	5.	Infusion set performance (including set failures as defined above and also glucose metrics, insulin doses, pump occlusion alarms and hyperglycemia trends) in subjects who use low doses (e.g., <25 units/day) of insulin and in subjects who experience frequent stops and start of pump use	
1036		8.4.6 Exploratory Endpoint	
1037	1	Hh A 1c change from baseline to the end of study participation	

1038		8.5 Analysis Datasets and Sensitivity Analyses	
1039 1040	1.	Only wears of the investigational infusion set will be included in the analysis (i.e., any wear of a personal infusion set will be excluded)	
1041 1042 1043	2.	All subjects with at least one wear of the investigational infusion set and all such wears will be included in the primary and secondary efficacy analyses. Subjects who complete at least six wear periods will be considered as "completers."	

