1044	3.	Since this is not a randomized trial, the intention-to-treat principle does not apply.	
1045	4.	All reported adverse events will be included in the safety analyses.	
1046		8.6 Analysis of the Primary Efficacy Endpoint(s)	
1047	Analysis will be done separately for each insulin type (Humalog and Novolog).		
1048 1049 1050	Kaplan-Meier estimates will be reported along with a curve used to estimate the proportion of infusion sets that last at least 7 days. Any infusion sets that are removed prior to day 7 without meeting the stated failure criteria will be treated as a censored observation.		
1051 1052 1053	A two-sided 95% confidence interval (95% CI) for the 7-day survival rate will be calculated with a bootstrap to account for the correlated data from having each subject wear multiple infusion sets. A corresponding p-value will be given for the null hypothesis that the true survival probability is 75%.		
1054		8.7 Analysis of the Secondary and Exploratory Endpoints	
1055 1056 1057 1058 1059	pooled Steadis device	ts from the primary analysis are comparable for Humalog and Novolog, then the data will be for secondary analyses. Otherwise, separate analyses will be done by insulin type. Percentage of Set infusion sets not withdrawn from use prior to 7 days (168 hours) as evidenced by the absence of failure, and as defined above, will be analyzed using the same statistical methods as described for the primary efficacy endpoint.	
1060 1061 1062 1063 1064	A paired t-test will be used to compare the central lab HbA1c values measured at the final study visit versus the Day 0 value. A two-sided 95% CI will be given for the mean difference. Only subjects with a central lab value at both times will be included in this analysis. Similar pre- post comparisons will be done with selected CGM metrics. These will include data from the final 14 days of the study compared with the baseline CGM data.		
1065	Survey	and pain assessment results will be tabulated.	
1066 1067		ner continuous and binary outcomes will be summarized as appropriate to their distributions (i.e., SD), median (IQR), or n (%)). Plots and 95% CI will be calculated for selected outcomes.	
1068 1069		metrics will be calculated over the entire study period (24-hour, daytime, and nighttime) and by week (24 hour only).	
1070	Hyperg	glycemia Trend in Days 1-3 versus after Day 3	

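### SAP 5 drops every mixed-insulin wear from the primary and key secondary analyses, which Protocol 8.5 does not provide for and which selects on how long the set lasted; the effect is small and one sentence repairs it

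*SAP*

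**What the plan says.** **SAP 5 (Outcome Measures):** if more "than one type of insulin is used during an infusion set wear period, that wear will be excluded" "from analyses of the Primary and Key Secondary Efficacy endpoints".

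**Protocol 8.5:** for subjects with at least one wear of the study set, "all such wears will be included in the primary and secondary efficacy analyses". The only wears it rules out are those of a personal infusion set.

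**Protocol 7.1:** if a subject moves from one of the two insulins to the other, "it will be noted in the case report form and analysed accordingly". It does not say how.

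**SAP 2:** "This SAP does not conflict with the study protocol statistics chapter".

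Four further provisions bear on the point.

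- Protocol 8.6 and SAP 6.2 run the primary analysis separately for Humalog and NovoLog users, by Kaplan-Meier. Protocol 8.6 adds: "Any infusion sets that are removed prior to day 7 without meeting the stated failure criteria will be treated as a censored observation".
- Protocol 3.1.2: "Subjects will be instructed to change the insulin cartridge every 48-72 hours", independently of the infusion set.
- Inclusion criterion 14 admits only subjects who expect no need to change insulin type. Protocol 7.3 nevertheless permits both insulins during the study.
- For the other endpoints, when they are analysed by insulin type, SAP 5 also drops mixed wears unless specified otherwise. SAP 6.3.2 (whole follow-up period), 6.3.2.1, 6.3.4 and 6.3.5 do specify otherwise: for CGM, occlusion-alarm and pain results, mixed wears are kept under the baseline insulin.

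**The concern.** There are two separate defects.

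The first is one of consistency. The SAP adds an exclusion from the primary analysis that the protocol's statistics chapter does not contain, and then states that the two agree.

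The second is statistical. Whether a wear is mixed is learned only after insertion, and it depends on survival. A set that fails at hour 30 cannot be mixed by a cartridge change at hour 48 or 72, whereas a set that lasts 168 hours passes two or three such changes. Removing the whole wear therefore removes long survivors more often than failures, which a Kaplan-Meier analysis cannot correct. It also discards known failure-free time on the first insulin, and a failure after the switch is counted in neither insulin's analysis.

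At stake is a small, avoidable bias in the primary estimate, and a rule that a regulatory reader will find in one document and not in the other.

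**Working it through.** **1. The plan's own power figure.** Inputs (Protocol 8.3, SAP 4): 120 subjects per insulin, 12 wears, within-subject correlation 0.4, null 75%, true rate 83%, two-sided 5%.

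- Design effect: 1 + 11 × 0.4 = 5.4. Effective n: 1440 / 5.4 = 266.7.
- Null standard error: √(0.75 × 0.25 / 266.7) = 0.0265. Alternative standard error: √(0.83 × 0.17 / 266.7) = 0.0230.
- With continuity correction: z = (0.08 − 1/(2 × 266.7) − 1.96 × 0.0265) / 0.0230 = 1.14, so power is 87.2% (stated: 87%).
- With 9 wears, effective n = 1080 / 4.2 = 257.1 and power is 85.8% (stated: 86%).

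The plan's figures reproduce. The standard error of the estimate at 83% is about 2.3 points.

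**2. What deletion does when switching is unrelated to failure.** Assumptions, none of them in the documents: constant failure hazard with 7-day survival 0.83; a probability q of changing insulin at each cartridge change; changes every 72 h (at 72 and 144 h) or every 48 h (at 48, 96 and 144 h).

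A survivor of 168 h is retained with probability (1 − q)^k, where k is 2 or 3. A failure is retained with probability (1 − q)^j, where j is the number of changes passed before it failed. The expected estimate after deletion is retained survivors / (retained survivors + retained failures).

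Worked case, 72 h and q = 1%:

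- S(72) = 0.9233, S(144) = 0.8524, S(168) = 0.83.
- Retained survivors: 0.83 × 0.9801 = 0.8135.
- Retained failures: 0.0767 + 0.0709 × 0.99 + 0.0224 × 0.9801 = 0.1688.
- Estimate: 0.8135 / 0.9823 = 82.81%.

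| Interval | q | Survivors deleted | Failures deleted | All wears deleted | Estimate | Shift (points) |
|---|---|---|---|---|---|---|
| 72 h | 0.5% | 1.0% | 0.3% | 0.89% | 82.91% | −0.09 |
| 48 h | 0.5% | 1.5% | 0.6% | 1.34% | 82.87% | −0.13 |
| 72 h | 1% | 2.0% | 0.7% | 1.77% | 82.81% | −0.19 |
| 48 h | 1% | 3.0% | 1.2% | 2.67% | 82.75% | −0.25 |
| 72 h | 5% | 9.8% | 3.4% | 8.67% | 82.01% | −0.99 |
| 48 h | 5% | 14.3% | 6.0% | 12.86% | 81.66% | −1.34 |

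A simulation of 4 million wears agrees. At q = 1%, deletion gives 82.7-82.8%, while keeping all wears or censoring at the switch gives 83.0%.

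**3. Is that range of q reasonable?** Per cohort of 1440 wears, q = 0.5% means 13-19 mixed wears (1440 × 0.89% to 1.34%) and q = 1% means 25-38. At q = 5% there would be 125-185, more than one per participant, which does not fit inclusion criterion 14.

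**4. Sensitivity to the hazard shape.** The shift is largest if all failures precede the first cartridge change. At q = 1% and 48 h: 0.83 × 0.9703 = 0.8053, and 0.8053 / (0.8053 + 0.17) = 82.57%, a shift of −0.43 points.

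**5. Bounds when switching may be related to failure.** Suppose 10% of 120 subjects switch once, each in mid-wear (assumption). Then 12 of 1440 wears (0.83%) are deleted, and 0.83 × 1440 = 1195.2 successes are expected before deletion. If all 12 were successes: 1183.2 / 1428 = 82.9%. If all 12 were failures: 1195.2 / 1428 = 83.7%.

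**6. Power.** Without continuity correction, power is 88.8% before deletion, 87.7-88.0% at q = 0.5% and 86.4-87.0% at q = 1%, allowing for both the lost wears and the lower estimate.

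**The case against.** The strongest reply is that the protocol left this gap for the SAP to fill. Protocol 7.1 foresees special handling of an insulin change. With separate analyses by insulin, a mixed wear belongs cleanly to neither, so a rule was required. The inclusive sentence in Protocol 8.5 is not literal either: the primary endpoint already leaves out sets removed within 8 hours. The choice also looks deliberate, because the SAP keeps mixed wears for CGM, occlusion-alarm and pain results but asks for single-insulin wears where the test is by insulin. And the effect is tiny: 0.25 points is about one-ninth of a standard error (0.25 / 2.3 = 0.11).

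Most of this stands, and it sets the weight of the point. It does not rescue whole-wear deletion. Protocol 7.1 does not mention exclusion, and a rule that uses the known time on the first insulin is available within the plan's own censoring approach.

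Three stronger readings are tempting and are not supported.

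- *That deletion favours the device*, because subjects would change insulin when glucose is unexplainedly high. The hyperglycemia guidance in Protocol 1.4 covers testing, correction boluses and set failure; it never mentions a change of insulin type. With unrelated switching the bias runs against the device.
- *That the two documents give different denominators for the 75% test.* The protocol never says in which insulin's analysis a mixed wear counts, so its by-insulin denominator is undefined rather than different.
- *That every switch costs one wear.* A change of insulin made when the set is replaced creates no mixed wear, so one per switch is an upper limit.

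**Conclusion.** The point holds as a minor defect of consistency and method. SAP 5 removes wears that Protocol 8.5 includes, without the protocol stating that rule and despite the assurance in SAP 2. The removal depends on survival after insertion.

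Under unrelated switching at an assumed 0.5-1% per cartridge change, the 7-day estimate falls by about 0.1 to 0.25 points, and by at most 0.43 at 1% if all failures came early. These figures rest on assumed switch rates, because the documents give none. If switching is related to failure, the documents do not determine the direction; the illustrative 10% case brackets the result between 82.9% and 83.7%.

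Power changes by about 1 to 2.5 points over the 0.5-1% range, and the shift is small beside the 8-point gap between 75% and 83%. The primary test is not in danger. The reason to act is that a better rule costs almost nothing.

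**What to change.** In SAP 5 and 6.2, replace the exclusion with this rule: a wear in which the insulin type changes stays in the Kaplan-Meier analysis of the insulin in use at insertion and is censored at the time of the change. Apply it to the key secondary endpoint as well, and state that the by-insulin tabulations count the wear under the insertion insulin.

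Add two items: a count of mixed wears by insulin type in SAP 8, and a sensitivity analysis that keeps the whole wear under the insertion insulin, so that a failure after the switch counts. Delayed entry of the wear into the second insulin's analysis is an option, not a requirement. It places one participant in both analyses and assumes that failure risk on the second insulin does not depend on the days already worn on the first.

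Bring Protocol 7.1 and 8.5 into line with the rule and correct the statement in SAP 2.

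Cost: a few sentences and one extra run of the same analysis. The time of the change must be captured; Protocol 7.1 says that a change is noted but not that its time is recorded. Censoring also assumes that switching is unrelated to impending failure, and the sensitivity analysis is there to check that.
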